#### 5.4.5            **Electrocardiogram**

Participants' maximum change from baseline in QTcF and QTcB will be categorized and the number and percentage of participants in each group will be summarized for study 20200491 and monotherapy cohorts of study 20160323 only. Unscheduled assessments will be included in the determination of the maximum change. The categories are  $\leq 30$  msec,  $> 30 - 60$  msec,  $> 60$  msec.

Participants' maximum post baseline values will also be categorized and the number and percentage of participants in each group will be summarized for study 20200491 and

monotherapy cohorts of study 20160323 only. The categories are  $\leq$  450 msec, > 450 – 480 msec, > 480 – 500 msec, > 500 msec.

No statistical analyses of ECG measurements are planned for tarlatamab arm of study 20210004.

#### **5.4.6 Clinical Laboratory Tests**

Shift tables between the worst postbaseline and baseline grades of selected laboratory parameters will be presented. Participant incidence of toxicity change of more than 3 grades from baseline will be summarized. Laboratory abnormalities that worsened from baseline will be summarized by all grades and grade 3 to 4.

Participant incidence of suspected Hy's law cases will be summarized using the following criteria:

- ALT or AST  $> 3 \times$  ULN at baseline and on-study.
- Total bilirubin  $> 2 \times$  ULN at baseline and on-study.
- (ALT or AST)  $> 3 \times$  ULN and (Total bilirubin  $> 2 \times$  ULN) and (ALP  $< 2 \times$  ULN) at baseline and on-study or within 30 days after a postbaseline ALT or AST (transaminases) elevation

Summaries of time from first tarlatamab administration (days) to first onset of grade 3 or higher increased will be provided for ALT, AST and total bilirubin, time from first tarlatamab administration (days) to first onset of grade 3 or higher decreased will be provided for hemoglobin, platelets and total neutrophils.

A listing of ALT, AST, ALP, and total bilirubin values at each time point will be produced for the participants suspected of Hy's law case.

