9.4.2.3.2 Laboratory Test Results

The analyses of safety laboratory endpoints will include summary statistics over time. Shifts in grades of safety laboratory values between the baseline and the worst on-study value will be tabulated.

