**5.2 Hypothesis/Estimation**

No formal hypothesis testing will be performed.

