#### **5.4.4 Adverse Events**

##### **5.4.4.1 All Adverse Events**

The MedDRA version **27.0** or later will be used to code all events categorized as adverse events to a system organ class and a preferred term. The severity of each adverse event will be graded using CTCAE version 5.0 for study 20200491 and tarlatamab arm of study 20210004. The severity of each adverse event for monotherapy cohorts of study 20160323 will be converted from CTCAE version 4.0 to 5.0 where possible. CRS and ICANS events from study 20200491 and tarlatamab arm of study 20210004 are graded according to ASTCT 2019. CRS and ICANS events from monotherapy cohorts of study 20160323 will be converted from Lee et al. 2014 to ASTCT 2019 where possible.

The participant incidence of adverse events will be summarized for all TEAEs, treatment-related TEAEs, serious TEAEs, grade 3 or higher TEAEs, fatal TEAEs, TEAEs leading to dose interruption and/or reduction of tarlatamab and TEAEs leading to discontinuation of tarlatamab.

Worst grade is derived as the maximum grade (per the applicable grading scale CTCAE / ASTCT) for each preferred term per participant.

Detail on the derivation of worst grade at event level will be provided in the TFL shell document.

Participant incidence of all TEAEs and TRAEs will be summarized as outlined in the [Table 3](#). When applicable, rows are sorted by system organ class (alphabetically) and

preferred term within system organ class (in descending order of frequency).

Overall summary of exposure-adjusted event rate of all TEAEs, serious TEAEs, grade 3 or higher TEAEs, fatal TEAEs, TEAEs leading to dose interruption and/or reduction of tarlatamab and TEAEs leading to discontinuation of tarlatamab will be produced. A separate overall summary of exposure-adjusted event rate of serious TEAEs will be provided.

Listing of TEAEs, listing of deaths during the studies will be produced with all the relevant fields.

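### On a 0 to 4 scale, the laboratory row in SAP 5.4.6 for changes above 3 grades counts only the worsening from grade 0 to grade 4, and it does not say that only worsening counts

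*SAP*

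**What the plan says.** SAP 5.4.6 (Clinical Laboratory Tests) plans three grade-based laboratory summaries, one after another. The first cross-tabulates grade before and after treatment, with no cut-off, for chosen parameters only. The second carries the cut-off at issue: "Participant incidence of toxicity change of more than 3 grades from baseline will be summarized". The third reports deterioration by the grade reached, whatever the size of the step: "Laboratory abnormalities that worsened from baseline will be summarized by all grades and grade 3 to 4".

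Neither document restates the cut-off of the second summary in an inclusive form. Protocol 9.4.2.3.2 (Laboratory Test Results) has no counterpart to it and asks only for the shift display: "Shifts in grades of safety laboratory values between the baseline and the worst on-study value will be tabulated".

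SAP 5.4.6 names no grading scale of its own. The nearest statement is in SAP 5.4.4.1, on adverse events: "The severity of each adverse event will be graded using CTCAE version 5.0 for study 20200491 and tarlatamab arm of study 20210004". The whole integrated analysis is descriptive; SAP 5.2 states "No formal hypothesis testing will be performed".

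**The concern.** A strict cut-off at 3 grades is unusual on a scale whose top laboratory grade is 4. It leaves room for one worsening only, from no abnormality to the highest grade. A participant who goes from normal to grade 3, or from grade 1 to grade 4, has deteriorated by three grades and is not counted. Elsewhere the SAP writes severity limits inclusively. In 5.4.6 itself, time to onset is planned for abnormalities of grade 3 or higher in ALT, AST, total bilirubin, hemoglobin, platelets and neutrophils. A fall in neutrophils from normal to grade 3 is therefore an event in the time-to-onset summary but not in the row for large grade changes in the same section.

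What is at stake is how one row is read. Its label refers to a change in toxicity, and a reader may take its count as the number of participants with any large deterioration, when it is the number with one particular shift. The sentence also speaks of change without giving a direction.

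**Working it through.** The plan states no count for this row, so there is no figure to reproduce. The check is an enumeration of grade pairs.

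**Inputs**

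- Cut-off: strictly more than 3 grades (SAP 5.4.6).
- Top laboratory grade: 4, taken from the grade 3 to 4 band in the same section.
- Lowest grade: 0 for normal. This is an assumption; the documents do not write out a 0 to 4 range.

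**Step 1: list the worsening shifts.** With baseline grade b and worst postbaseline grade p, worsening means p > b.

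| Baseline b | Possible p | Change p − b |
|---|---|---|
| 0 | 1, 2, 3, 4 | 1, 2, 3, 4 |
| 1 | 2, 3, 4 | 1, 2, 3 |
| 2 | 3, 4 | 1, 2 |
| 3 | 4 | 1 |

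Total: 4 + 3 + 2 + 1 = 10 worsening shifts.

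**Step 2: apply each rule.**

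| Rule | Shifts counted | Number |
|---|---|---|
| p − b > 3 (as written) | 0 to 4 | 1 of 10 |
| p − b ≥ 3 | 0 to 3, 0 to 4, 1 to 4 | 3 of 10 |
| Worsened to grade 3 or 4 (third summary in 5.4.6) | 0 to 3, 1 to 3, 2 to 3, 0 to 4, 1 to 4, 2 to 4, 3 to 4 | 7 of 10 |

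**Step 3: who can be counted.** The largest possible worsening from baseline grade b is 4 − b. The condition 4 − b > 3 requires b = 0. A participant with any abnormality of grade 1 or more at baseline cannot enter the row for that parameter, whatever happens on treatment. With 4 − b ≥ 3, baseline grades 0 and 1 both qualify.

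**Step 4: does the result depend on the assumed scale?** For the two excluded shifts, no: 3 − 0 = 3 and 4 − 1 = 3, and 3 is not greater than 3 on any scale. On a 0 to 5 scale there are 5 + 4 + 3 + 2 + 1 = 15 worsening shifts. The written rule would count 0 to 4, 0 to 5 and 1 to 5, and would still omit 0 to 3 and 1 to 4. Only the statement that 0 to 4 is the sole shift counted depends on the 0 to 4 range.

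**Step 5: direction.** If change is read as a size in either direction, the rule also admits the improvement 4 to 0. If the general definition of change in SAP Section 3 is applied (the later value less the baseline value), 4 to 0 gives 0 − 4 = −4 and does not qualify. The row itself does not say which applies.

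**Step 6: where the excluded shifts still appear.** In the shift tables, 0 to 3 and 1 to 4 are separate cells, but only for the parameters selected. Both also fall in the grade 3 to 4 worsening summary, whose sentence is not limited to selected parameters. That summary pools them with smaller steps such as 2 to 3, so it does not isolate large changes.

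**The case against.** The case for leaving the text alone is substantial. The sentences on either side of the cut-off already report both excluded shifts, the protocol asks for shift tabulations with no cut-off, and no test, stopping rule or estimand uses this row. A row that isolates the most extreme shift is narrow but coherent beside full shift tables. Nothing in the documents shows that an inclusive cut-off was meant, and the choice of cut-off for a supplementary count is partly preference. The grading range is inferred, and SAP 5.4.1 leaves data derivation to individual study SAPs that are not available here. Finally, the comparison of 1 shift with 3 counts types of shift, not participants, and it treats three grades as the mark of a large change.

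Most of this stands, and it limits the size of the point. It does not answer two things. The label describes a class of changes while the rule reduces to one shift, and the direction is not stated in the row. The other summaries do not supply the missing count either: the shift tables cover selected parameters only, and the grade 3 to 4 summary mixes one-grade steps with three-grade jumps.

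**Conclusion.** The point holds as a minor one. Assuming laboratory grades 0 to 4, the row counts 1 of 10 possible worsening shifts. It leaves out the three-grade worsenings 0 to 3 and 1 to 4 and does not restrict the change to worsening. The exclusion of those two shifts needs no assumption about the range; the reduction to a single shift does.

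A reader might infer more, and the documents do not support it:

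- *That large laboratory deteriorations are lost from the safety analysis.* They are not. Both shifts appear elsewhere in SAP 5.4.6, and the loss is confined to this row.
- *That the row will be nearly empty, or that its low count will give false reassurance.* The documents contain no laboratory shift frequencies. Neutropenia is among the adverse drug reactions in Protocol 2.3, and Protocol Table 6-2 provides for grade 4 neutropenia, so an empty 0 to 4 cell cannot be presumed.
- *That the sponsor plainly meant an inclusive cut-off.* The inclusive limits used elsewhere make this plausible, but no text establishes it.

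The number of participants affected cannot be estimated from the documents.

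**What to change.** In SAP 5.4.6, replace the cut-off phrase with *worsening of 3 or more grades from baseline*. This settles both the threshold and the direction. On a 0 to 4 scale the row would then count 0 to 3, 0 to 4 and 1 to 4.

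If the sponsor did intend only the most extreme shift, keep the rule but label the row *grade 0 to grade 4*, so that its count is not read as covering all large deteriorations.

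The cost is one phrase in the SAP and the matching row label in the table shell. No data collection or other analysis changes; only the counts in this row may differ.

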#### **5.4.7 Physical Measurements**

Physical measurement data will be listed and reviewed for each participant.

#### **5.4.8 Vital Signs**

The incidence and percentage of abnormal changes in all vital signs (including systolic/diastolic blood pressure, heart rate, respiratory rate, oxygen saturation and body temperature) will be tabulated.

#### **5.4.9 Antibody Formation**

The incidence and percentage of participants who develop anti-tarlatamab antibodies at any time will be tabulated. Summaries of positive anti-tarlatamab antibody test results over time may be provided. Overall summary of TEAEs and incidence of TEAEs by system organ class and preferred term may be tabulated by anti-tarlatamab antibodies.

#### 5.4.10 Exposure to Concomitant Medication

The number and proportion of participants receiving therapies of CRS will be summarized by preferred term as coded by the World Health Organization Drug (WHO DRUG) dictionary.

#### 5.5 Postmarketing Requirement

In order to meet the postmarketing requirement from FDA, analyses of adverse events for different periods, severity, and outcome of the known serious risks of CRS and ICANS will be further characterized based on the integrated safety analysis of data from participants with extensive stage SCLC. A comprehensive analysis will be included from all available data sources including but not limited to participant-level and pooled analyses of study 20200491 and monotherapy cohorts of study 20160323 and tarlatamab arm of study 20210004.

Summaries of all EOIs, serious EOIs, time to onset of EOIs from first tarlatamab administration (days), time to onset of serious EOIs from first tarlatamab administration (days), time to onset of EOIs from last prior tarlatamab administration (days), time to onset of serious EOIs from last prior tarlatamab administration (days), duration of EOIs (days) and duration of serious EOIs (days) will be provided by following periods:

- Period 1: From cycle 1 day 1 to 90 days after cycle 1 day 1 or end of treatment, whichever occurs earlier.
- Period 2: From 90 days after cycle 1 day 1 to end of treatment.
- Period 3: From end of treatment to end of safety follow up.
- Period 4: From end of safety follow up to end of long term follow up or end of study, whichever occurs later .

Similar summaries above will be repeated for pituitary dysfunction events by period 3 and period 4. Pituitary dysfunction events are identified by Global Safety Officer using preferred terms coded MedDRA version **27.0** or later.

Severity and outcome of the known serious risk of CRS, ICANS and neurologic toxicity are mentioned in [section 5.4.4.2](#).

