^b On-study cycle 1 visits may be completed within \pm 1 day.

^c Additional on-treatment pregnancy testing may be performed at the investigator's discretion if there is suspicion that a female subject is pregnant or per local laws and regulations.

^d If screening local labs are obtained within 48 hours prior to C1D1 dose, pre-infusion C1D1 samples do not have to be repeated. Where applicable, C1 D8 and D15 local labs may be obtained within 48 hours prior to dose (D8 and D15). Results must be reviewed prior to study drug administration.

^e TSH and FT4, lipase and amylase if obtained within 72 hours prior to C1D1 dose, pre-infusion C1D1 samples do not have to be repeated. At subsequent visits, labs may be obtained up to 72 hours prior to dose. Results must be reviewed prior to study drug administration.

Table 1-2. Tarlatamab Schedule of Activities – Cycle 2+

Procedure ^a	Study Treatment ^b							As clinically indicated	EOT	SFU ^c	LTFU ^d	Notes
	Cycle 2			Cycle 3+			Q6W ^h					
Week	1	2	3	4	1	2	3	4				
Day	1	8	15	22	1	8	15	22				
GENERAL AND SAFETY ASSESSMENTS												
Physical examination	(X)	X	(X)	X				X	X	X		Physical exam must be completed prior to start of infusion on treatment days. (X): Must include weight at each day 1
Neurological examination	X	X	X	X				X	X	X		Neurological exam must be completed prior to start of infusion on treatment days.
ECOG PS	X		X					X	X	X		
Vital signs, pulse oximetry	X	X	X	X				X	X	X		
12-lead ECG								X	X	X		Single ECGs
ECHO or MUGA								X				
Vital status (survival status)								X	X	X		
Subsequent anti-cancer therapy								X	X	X		
Adverse events							continuous					Refer to Section 8.4.6.1.1.
												During the LTFU phase, serious adverse events suspected to be related to investigational product will be reported to Amgen.
Serious adverse events												After end of study, if the investigator becomes aware of serious adverse events suspected to be related to investigational product, then these serious adverse events will be reported to Amgen.
Prior/Concomitant therapies review							continuous					Please refer to Section 8.4.6.1.2 and 8.4.6.1.3 for additional details.

Footnotes defined on last page of this table.

Table 1-2. Tarlatamab Schedule of Activities – Cycle 2+

Procedure ^a	Study Treatment ^b							Notes				
	Cycle 2			Cycle 3+			As clinically indicated					
Week	1	2	3	4	1	2	3	4	Q6W ^h	EOT	SFU ^c	LTFU ^d
Day	1	8	15	22	1	8	15	22				
LABORATORY ASSESSMENTS												

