8.1.5 Long-term Follow-up

Following the SFU visit, there will be an LTFU period for clinical evaluation of disease status and survival. Subjects will be followed via telephone, clinic visit, or chart review to assess for survival and/or the commencement of subsequent cancer therapy every 12 weeks (\pm 14 days) from the SFU visit (or last imaging visit, whichever is later) for up

to 3 years after the last subject is enrolled, or 1 year from the subject's last dose of study treatment, whichever is later.

Vital status (survival status), imaging and tumor assessment (until radiographic disease progression), subsequent anticancer treatment (ie, subsequent therapies taken for SCLC), serious adverse events suspected to be related to study treatment, and urine pregnancy test **60** days after last dose of tarlatamab will be collected.

The assessments that will be collected during the LTFU are designated in the Schedule of Activities (Section 1.3).

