8.4.6 Adverse Events and Serious Adverse Events

The method of recording, evaluating, and assessing causality of adverse events, and serious adverse events and the procedures for completing and transmitting serious adverse event reports are provided in [Section 11.4 with the following exceptions:](#)

CRS and ICANS will be graded according to American Society for Transplantation and Cellular Therapy (Lee et al, 2019) as described in [Table 6-2](#) and [Section 11.11](#).

8.4.6.1 Time Period and Frequency for Collecting and Reporting Safety Event Information**8.4.6.1.1 Adverse Events**

The adverse event grading scale to be used for this study will be the CTCAE v5.0 and is described in Section 11.4.

The investigator is responsible for ensuring that all adverse events observed by the investigator or reported by the subject that occur after the first dose of investigational product(s) or noninvestigational product(s)/auxiliary medicinal product(s) through the SFU visit or **60** days after the last dose of investigational product(s) or non-investigational product(s)/auxiliary medicinal product(s), whichever is later, are reported using the Events CRF.

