8.4.6.1.2 Serious Adverse Events

The investigator is responsible for ensuring that all serious adverse events observed by the investigator or reported by the subject that occur after signing of the informed consent through the SFU visit or **60** days after the last dose of investigational product(s) or noninvestigational product(s)/auxiliary medicinal product(s), whichever occurs later, are reported using the Events CRF.

All serious adverse events will be collected, recorded, and reported to the sponsor or designee immediately and no later than 24 hours of the investigator's awareness of the event, as indicated in Section 11.4. The investigator will submit any updated serious adverse event data to the sponsor immediately and no later than 24 hours of it being available.

Since the criteria the CTCAE grading scale differs from the regulatory criteria for serious adverse events, if adverse events correspond to grade 4 CTCAE toxicity grading scale criteria (eg, laboratory abnormality reported as grade 4 without manifestation of life-threatening status), it will be left to the investigator's judgment to also report these abnormalities as serious adverse events. For any adverse event that applies to this situation, comprehensive documentation of the event's severity must be recorded in the subject medical records.

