8.4.6.1.3 Serious Adverse Events After the Protocol Required Reporting Period

During the LTFU period, if the investigator becomes aware of serious adverse events suspected to be related to the investigational product after the protocol-required reporting period (as defined in Section 8.4.6.1.2 is complete, then these serious adverse

events will be reported to Amgen. The investigator will report serious adverse events to Amgen immediately and no later than 24 hours following the investigator's awareness of the event on the Events CRF.

There is no requirement to actively monitor study subjects after the study has ended with regards to study subjects treated by the investigator. However, if the investigator becomes aware of serious adverse events suspected to be related to investigational product, then these serious adverse events will be reported to Amgen immediately and no later than 24 hours following the investigator's awareness of the event.

Serious adverse events reported after the end of the study will be captured within the safety database as clinical **study** cases and handled accordingly based on relationship to investigational product.

If further safety related data is needed to fulfill any regulatory reporting requirements for a reportable event, then additional information may need to be collected from the subject's records after the subject ends the study.

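### SAP 5.5 tabulates Period 4 events of interest as in Periods 1 to 3, but Study 20210004 collects new onsets after safety follow-up only if serious and suspected related

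*SAP*

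**What the plan says.** SAP 5.5 is written to meet an FDA postmarketing requirement on CRS and ICANS. It lists one set of summaries (all EOIs, serious EOIs, times to onset from the first and the last prior dose, durations) and applies it to four periods without distinction. Period 3 runs from end of treatment to end of safety follow-up. Period 4 runs "From end of safety follow up to end of long term follow up or end of study, whichever occurs later". For pituitary events: "Similar summaries above will be repeated for pituitary dysfunction events by period 3 and period 4". SAP 5.3.1 bases all safety endpoints on the safety analysis set, and SAP 5.2 rules out formal testing. SAP section 3 leaves the definitions of safety follow-up and long-term follow-up (LTFU) to the individual study SAPs.

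For Study 20210004, Protocol 8.4.6.1.1 requires all adverse events after the first dose of investigational product or "noninvestigational product(s)/auxiliary medicinal product(s) through the SFU visit or" 60 days after the last dose, whichever is later. Protocol 8.4.6.1.2 requires all serious adverse events "that occur after signing of the informed consent through the SFU visit" or 60 days after the last dose, again the later of the two.

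After that the rule narrows. The safety items that Protocol 8.1.5 lists for LTFU are "serious adverse events suspected to be related to study treatment, and urine pregnancy test". The tarlatamab Schedule of Activities (Table 1-2) says: "During the LTFU phase, serious adverse events suspected to be related to investigational product will be reported to Amgen". Protocol 8.4.6.1.3 adds a condition: such events are reported "if the investigator becomes aware of serious adverse events suspected to be related to the investigational product". On the contacts themselves, Protocol 8.1.5 says: "Subjects will be followed via telephone, clinic visit, or chart review to assess for survival and/or the commencement of subsequent cancer therapy".

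**The concern.** The SAP gives Period 4 the same row labels as the earlier periods, yet the protocol changes what is collected exactly at the boundary between Periods 3 and 4. A reader who sees few events in a Period 4 all-EOIs row will take this as evidence that late events are rare. In 20210004 it may only mean that non-serious and unrelated onsets were no longer collected. The pituitary summaries are the most exposed, because Periods 3 and 4 are the only periods planned for them.

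At stake is what the late-toxicity tables can support in an output meant for a regulator. The error runs one way: missing onsets make late toxicity look rarer. The point matters less for CRS, which Protocol 4.4 says occurs mostly after the first two infusions, and more for ICANS, other neurologic events and pituitary events.

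**Working it through.** The plan states no figure to reproduce. The check sets the collection rules of 20210004 against the planned rows, for new onsets only.

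| New onset in 20210004 | Periods 1–3 | Period 4 |
|---|---|---|
| Non-serious, any cause | collected | not collected |
| Serious, not suspected related | collected | not collected |
| Serious, suspected related | collected | collected |

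Sources: Protocol 8.4.6.1.1 and 8.4.6.1.2 for Periods 1–3; Protocol 8.1.5, 8.4.6.1.3 and Table 1-2 for Period 4.

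**Row content.** In Periods 1–3 the all-EOIs row holds all three kinds and the serious row holds the last two. In Period 4 both rows hold only the last kind, so they contain the same new onsets. The all-EOIs label is then wrong. The serious label is true as to seriousness but silent about the relatedness condition.

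**Why only new onsets.** Protocol 8.4.6.3 follows every reported event to resolution or stabilization. A non-serious event that began earlier can therefore still be open in Period 4.

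**Boundary.** Protocol 8.1.4 and Table 1-2 place the safety follow-up visit at 60 (+5) days after last dose; the schema footnote in Protocol 1.2 says ±5. If the visit falls at day 55 and the study SAP ends safety follow-up at the visit, up to 60 − 55 = 5 days of full collection fall in Period 4. This does not change the result.

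**Size of the under-count.** Let s be the share of true Period 4 onsets that are serious, r the share of serious ones suspected related, and a the probability that the investigator learns of them.

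- Captured share of the all-EOIs row = s × r × a
- Captured share of the serious-EOIs row = r × a

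The documents give none of the three. Purely to show how widely the answer moves, assume s = 0.10 to 0.50, r = 0.50 to 0.90 and a = 0.50 to 1.00:

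- all-EOIs row: 0.10 × 0.50 × 0.50 = 2.5% to 0.50 × 0.90 × 1.00 = 45%
- serious-EOIs row: 0.50 × 0.50 = 25% to 0.90 × 1.00 = 90%

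These are assumptions, not estimates.

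**A true fall is also expected.** The Amendment 4 summary equates 60 days with 5 half-lives, so about 0.5^5 = 3.1% of drug remains at the start of Period 4. A drop from Period 3 to Period 4 mixes washout with the change in collection, and the planned rows cannot separate them.

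**Denominator.** If a share f of the safety analysis set enters Period 4, a percentage on the full set equals f times the percentage among entrants. Participants who die or are cut off earlier stay in the denominator but cannot contribute an event. The documents do not give f.

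**The case against.** The strongest reply is that SAP 5.5 is descriptive, plans no test across periods, and defers follow-up definitions and derivations to the study SAPs (SAP section 3 and 5.4.1). Neither those SAPs nor the table shells were supplied, so a footnote on the LTFU rule may already exist. That limits what can be said about the final tables. It does not remove the mismatch: no derivation rule recovers events that were never collected, and identical labels in adjacent periods invite the comparison whether or not it is tested.

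A reader might infer several stronger things that the documents do not support:

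- *Both Period 4 rows are mislabelled.* A serious, suspected-related event is a serious EOI. That row is incomplete, not mislabelled.
- *Every LTFU rule depends on the investigator becoming aware.* For LTFU, only Protocol 8.4.6.1.3 says so. Protocol 8.1.5 says the events will be collected, and Table 1-2 attaches awareness to the time after end of study. Protocol 8.1.5 also describes LTFU as covering clinical evaluation of disease status, not survival alone.
- *The SAP has no denominator.* SAP 5.3.1 supplies one. The difficulty is that it suits Period 4 poorly.
- *Pooling in SAP Table 1 conceals the restriction.* SAP 5.5 also promises participant-level analyses, so concealment is not shown.
- *The length of Period 4 measures the defect.* With one year of follow-up after last dose, Period 4 lasts 365 − 65 = 300 to 365 − 60 = 305 days, much longer than Period 3. That shows unequal length only, and it would remain if every event were collected. One year is also the shorter limb of the rule: Protocol 8.1.5 follows participants to the later of that date or 3 years after the last enrolment.

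**Conclusion.** The point holds for new onsets in Study 20210004 after the later of the safety follow-up visit or 60 days after last dose. The Period 4 all-EOIs row is mislabelled. The serious-EOIs row is limited to suspected-related events without saying so. Neither row, nor the Period 4 pituitary row, is comparable with earlier periods. The safety analysis set as denominator would also count participants who never reached Period 4.

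The direction is toward apparent late safety. The size cannot be computed from the documents. The finding covers only the 20210004 contribution, because the LTFU rules of 20200491 and 20160323 were not supplied. It should be corrected because it changes what the late-toxicity tables can conclude, but it affects no hypothesis test.

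**What to change.** 1. For 20210004, label Period 4 new onsets 'serious, suspected related'. Show events carried over from earlier periods on separate rows; do not delete them.
2. Show Period 4 by study, with each study's LTFU collection rule in a footnote. Keep fuller rows for any study that collects more.
3. Add serious-and-related rows for the earlier periods (Periods 1–3 for EOIs, Period 3 for pituitary events), so that any reading across periods is like for like.
4. Use participants entering each period, with their person-time, as the denominator for the by-period summaries.

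The cost is SAP wording and some extra table work. No new data are needed: Protocol 11.4 already makes seriousness and relatedness mandatory fields for each event. The downside is a narrower stated scope for late toxicity in 20210004, which is the scope its data can support.
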